5.3.3. Analyses for Continuous Data

Descriptive statistics, such as the mean, standard deviation, coefficient of variation, median, minimum, and maximum values, will be provided for continuous endpoints.

5.4. Methods to Manage Missing Data

5.4.1. Missing Dates

In compliance with Pfizer standards, if the day of the month is missing for any date used in a calculation, the 1st of the month will be used to replace the missing date unless the calculation results in a negative time duration (eg, date of onset cannot be prior to day one date). In this case, the date resulting in 0 time duration will be used. Pfizer standards are also used if both month and day are missing (Jan 1 unless negative time duration). This excludes the pharmacokinetic, ECG, **CCI** analyses, which will only use the actual date collected or if date not available deem the data missing.

5.4.2. Efficacy Analysis

For the time-to-event endpoints, the missing data handling method will be censoring. Censoring rules for time-to-event endpoints are detailed in [Section 9.2](#).

5.4.3. Pharmacokinetics

Concentrations below the limit of quantification

In all data presentations (except listings), concentrations below the limit of quantification (BLQ) will be set to zero. (In listings BLQ values will be reported as “<LLQ”, where LLQ (ie, lower limit of quantification) will be replaced with the value for the LLQ).

Deviations, missing concentrations and anomalous values

Patients who experience events that may affect their PK (eg, incomplete dosing) may be excluded from the PK analysis.

In summary tables and plots of median profiles, statistics will be calculated with concentrations set to missing if one of the following cases is true:

1. A concentration has been reported as ND (ie, not done) or NS (ie, no sample),
2. A deviation in sampling time is of sufficient concern or a concentration has been flagged anomalous by the pharmacokineticist.

Note that summary statistics will not be presented at a particular time point if more than 50% of the data are missing.

An anomalous concentration value is one that, after verification of bioanalytical validity, is grossly inconsistent with other concentration data from the same individual or from other subjects. For example, a BLQ concentration that is between quantifiable values from the same dose is considered as anomalous. Anomalous concentration values may be excluded from PK analysis at the discretion of the PK analyst.

Pharmacokinetic parameters

Actual PK sampling times will be used in the derivation of PK parameters. If a PK parameter cannot be derived from a subject's concentration data, the parameter will be coded as NC (ie, not calculated). (Note that NC values will not be generated beyond the day that a subject discontinues).

In summary tables, statistics will not be presented for a particular treatment group if more than 50% of the data are NC. For statistical analyses, PK parameters coded as NC will also be set to missing.

If an individual subject has a known biased estimate of a PK parameter, this will be footnoted in summary tables and will not be included in the calculation of summary statistics or statistical analyses.

CCI

6. ANALYSES AND SUMMARIES

For efficacy related endpoints in this study, the following analysis plan may be implemented if the data is sufficient. For tumor response assessment, PCWG2 will be used for prostate cancer patient and RECIST 1.1 will be used for other tumor types.

Endpoint	CCI	Part 2
ORR		Both
PFS		Unconfirmed*
DOR		Both
TPP		Unconfirmed*
TTR		Both

Note: "Both" in the above table represents both unconfirmed and confirmed tumor assessments.

*: Confirmation for progressed disease is not applicable in RECIST 1.1.

In the "unconfirmed" analyses (ie, tumor response or progression without confirmation required), all tumor assessments data will be included for analyses. Specifically, regardless if a patient's tumor response or progression is subsequently confirmed or not, the patient data will all be included in the "unconfirmed" analyses. This is a more comprehensive analysis where tumor confirmation is not required and not taken into account. For example in the ORR analysis, if a patient achieved CR or PR, regardless it is subsequently confirmed or not, the patient will be included in the numerator.

In the "confirmed" analyses (ie, tumor response with confirmation required), only those tumor assessments data that's subsequently confirmed by a consecutive tumor scan will be considered as a "success" or "event" and be included for analyses as appropriate. For example, in the ORR analysis, a patient will only be counted in the numerator (the "success") if the tumor response (CR or PR) is subsequently confirmed. If a patient's tumor response is not subsequently confirmed, the patient will still be included in the denominator (the population set) but will not be included in the numerator (the "success").

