Soft-tissue lesions: Use RECIST with caveats,

- Only report changes in lymph nodes that were ≥ 2.0 cm in diameter at baseline;
- Record changes in nodal and visceral soft tissue sites separately;
- Record complete elimination of disease at any site separately;
- Confirm favorable change with second scan.

Bone:

- Record outcome as new lesion or no new lesions

Criteria for Evidence of Radiographic Progression

Bone disease will be assessed for progressive disease only by PCWG2. The documentation required for the determination of radiographic progression is shown in the table below.

Date Progression Detected ^[1]	Criteria for Progression	Criteria to Confirm Progression	Criteria to Document Disease Progression on Confirmatory Scan
Week 9	Bone lesions: 2 or more new lesions compared to screening bone scan by PCWG2	Timing: At least 6 weeks after progression identified or at Week 16 visit ^[2]	2 or more new bone lesions on bone scan compared to Week 8 scan
	Soft tissue lesions: Progressive disease on CT or MRI by RECIST v1.1	No confirmatory scan required for soft tissue disease progression	No confirmatory scan required for soft tissue disease progression
Week 18 or later	Bone lesions: 2 or more new lesions on bone scan compared to Week 8 bone scan	Timing: At least 6 weeks after progression identified or at next imaging time point ^[2]	Persistent or increase in number of bone lesions on bone scan compared to prior scan ^[3]

Date Progression Detected ^[1]	Criteria for Progression	Criteria to Confirm Progression	Criteria to Document Disease Progression on Confirmatory Scan
	Soft tissue lesions: Progressive disease on CT or MRI by RECIST v1.1	No confirmatory scan required for soft tissue disease progression	No confirmatory scan required for soft tissue disease progression

[1] Progression detected by bone scan at an unscheduled visit either before Week 8 or between scheduled visits will require a confirmatory scan at least 6 weeks later and should follow confirmation criteria outlined in the table for the next scheduled scan.

[2] Confirmation must occur at the next available scan.

[3] For confirmation, at least 2 of the lesions first identified as new must be present at the next available scan (confirmation scan).

Disease progression in bone must be confirmed at least 6 weeks later, as per PCWG2. See table below for the timing of confirmatory imaging requirements.

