Confirmatory Imaging Requirements for Patients With CRPC Based on RECIST v1.1 and PCWG2

Disease Site	Response	Progression ^[1]
Soft tissue	Must be confirmed at least 4 weeks later	No confirmation required
Bone	Not applicable	Must be confirmed at least 6 weeks later

[1] To inform permanent treatment discontinuation.

Objective Response Status at Each Evaluation

Target Lesions	Non-target Disease	New Lesions	Objective status
CR	CR	No	CR
CR	Non-CR/Non-PD	No	PR
CR	Indeterminate or Missing	No	PR
PR	Non-CR/Non-PD, Indeterminate, or Missing	No	PR
SD	Non-CR/Non-PD, Indeterminate, or Missing	No	Stable
Indeterminate or Missing	Non-PD	No	Indeterminate
PD	Any	Yes or No, including bone determination	PD
Any	PD	Yes or No	PD
Any	Any	Yes	PD

If there is a protocol deviation and a patient has been enrolled allows enrollment of patients with only non-target disease, the following table will be used:

Objective Response Status at Each Evaluation for Patients With Non-Target Disease Only

Non-target Disease	New Lesions	Objective status
CR	No	CR
Non-CR/Non-PD	No	Non-CR/Non-PD
Indeterminate	No	Indeterminate
Unequivocal progression	Yes or No	PD
Any	Yes	PD

Procedures for Assessing PSA Response/Progression Post Study Treatment

PSA measurements will be performed on C1D1 (± 14 days) and Day 1 of Cycle 4, 7, 10 and every third cycle thereafter, as well as at the End of Treatment visit. Increases and decreases will be tracked in order to assess disease response. The PSA readings on its own will not be used to define progression in this protocol. PSA response and PSA progression will be defined according to the consensus guidelines of the PCWG2:

- PSA partial response is defined as a $\geq 50\%$ decline in PSA from Cycle 1 Day 1 (baseline) PSA value. This PSA decline must be confirmed to be sustained by a second PSA value obtained 4 or more weeks later.
- PSA progression date is defined as the date that a $\geq 25\%$ increase and an absolute increase of ≥ 2 ng/mL above the nadir is documented, which is confirmed by a second consecutive value obtained 4 or more weeks later. The first PSA reading will be obtained at week 12.

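### SAP Section 6 counts progression unconfirmed for Part 2 PFS and TTP on RECIST 1.1 grounds, although the mCRPC criteria in SAP 9.5 and protocol Appendices 5 and 7 count bone progression only after a confirming scan

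*SAP*

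**What the plan says.** The table in SAP Section 6 lists ORR, DOR and TTR for Part 2 both with and without confirmation, but PFS and TTP (printed TPP) without confirmation only. The footnote reads "Confirmation for progressed disease is not applicable in RECIST 1.1". The text below it includes progression whether or not a later scan confirms it, and adds: "This is a more comprehensive analysis where tumor confirmation is not required and not taken into account". The confirmed analysis is described for tumor response only. The same section states that "PCWG2 will be used for prostate cancer patient and RECIST 1.1 will be used for other tumor types".

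SAP 9.5 separates the two disease sites. For soft tissue: "No confirmatory scan required for soft tissue disease progression". For bone: "Bone disease will be assessed for progressive disease only by PCWG2", and a table sets out what is needed to determine radiographic progression. For new lesions at the first on-study scan (row labelled week 9, criteria referring to week 8), the confirmatory scan must show "2 or more new bone lesions on bone scan compared to Week 8 scan". For later findings, the lesions must persist or increase at the next scan. Protocol Appendix 7 repeats this table. The Appendix 5 worksheet ends in the conclusion of no radiographic progression by bone scan if its second step is not met.

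SAP 9.2, Table 1, dates a PFS or DOR event at the first assessment showing objective progression. Neither Table 1 nor Table 2 (TTP) has a row for bone findings.

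**The concern.** The reason given in Section 6 belongs to a criterion that does not govern bone in these patients. Parts 2A and 2B enrol only mCRPC, so RECIST 1.1 alone cannot justify ignoring confirmation there. As a result the SAP holds two rules for the same bone scan: Section 6 counts it at once, while 9.5 waits for a second scan and may then discard it.

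At stake are the event dates for PFS and TTP. The end of DOR is also affected, because it shares Table 1. With 10 and 20 patients a single patient visibly moves a Kaplan-Meier curve, and two analysts could defend different dates from the same data. These endpoints are secondary and descriptive, SAP 5.1 states no hypotheses, and no error rate is involved.

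**Working it through.** The plan gives no event count, precision or expected median for PFS or TTP, so there is no figure to reproduce. The check compares the rules on one case and then sizes one affected patient.

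**One case under each rule.** Week-8 bone scan: 2 new lesions compared with screening. Week-16 scan: the same 2 lesions and no others. No soft-tissue progression.

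- SAP 9.5 and Appendix 7: the week-16 scan must show at least 2 lesions that are new since week 8. It shows 0, so progression is not documented.
- Appendix 5 worksheet, question 1 at week 16 (2 or more new lesions compared with week 8?): no. The form concludes that there is no radiographic progression by bone scan.
- SAP Section 6 with Table 1 of 9.2: progression is included whether or not it is confirmed, and is dated at the first assessment showing it. Result: an event at week 8.

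A finding after week 8 that is absent at the next scan gives the same disagreement. Soft tissue does not: Section 6 and 9.5 agree there.

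**Direction.** Section 6 can only add an event that 9.5 would not count, or date one earlier. PFS and TTP can therefore only become shorter.

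**Size per affected patient.** Inputs: N = 20 (Part 2B) and N = 10 (Part 2A), from SAP 5.2.2 and 5.2.3. Assumption: all are in the mITT set and none is censored before week 8. Each affected patient then lowers the week-8 Kaplan-Meier estimate by 1/N:

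- Part 2B: 1/20 = 5 percentage points
- Part 2A: 1/10 = 10 percentage points

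**Against sampling error.** SE = √[S(1 − S)/N]. S is not in the documents. Assuming exponential PFS with a median of 24 weeks, S(8) = 0.5^(8/24) = 0.79; with a median of 16 weeks, S(8) = 0.5^(8/16) = 0.71.

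| Week-8 S | SE, N = 20 | SE, N = 10 |
|---|---|---|
| 0.79 | √(0.79 × 0.21/20) = 0.091 | √(0.79 × 0.21/10) = 0.129 |
| 0.71 | √(0.71 × 0.29/20) = 0.101 | √(0.71 × 0.29/10) = 0.143 |

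One patient's shift is below one SE in all four cells. In general, 1/N < SE requires S(1 − S) > 1/N. That holds for S between 5.3% and 94.7% when N = 20, and between 11.3% and 88.7% when N = 10.

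**Total effect.** With k affected patients the shift is k/N. The documents give no basis for k.

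**The case against.** The best defence is that nothing unconfirmed ever reaches the analysis. Protocol 7.8 bases the analysis on investigator assessments, and SAP 6.3.1 lists the investigator's response and progression date. The investigator signs the Appendix 5 worksheet, the objective-status table in 9.5 refers to the bone determination, and Table 1 asks for objective progression. If the investigator applies the worksheet before declaring progression, the patient in the case above is never recorded as progressed. This is a fair reading, and it means that miscounting is possible rather than certain. It does not settle the matter, because Section 6 states the opposite rule and nowhere says that PCWG2 status comes first.

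A second defence is that confirmation serves treatment decisions only. The sentence "Disease progression in bone must be confirmed at least 6 weeks later, as per PCWG2" leads into a table whose progression column carries the footnote "To inform permanent treatment discontinuation". That footnote limits that table, so the sentence is weak independent support. It does not reach the radiographic-progression table or the worksheet, which define progression itself. The point rests on those two.

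Third, a reader might infer that leaving soft-tissue progression unconfirmed is settled. It agrees with 9.5 and Appendix 7, but the mCRPC text of protocol 7.8 requires any progression to be confirmed at least 4 weeks later, absent rapid clinical deterioration, with no split by site. The documents do not say whether that sentence defines the endpoint.

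**Conclusion.** The conflict is real for bone and comes from the SAP's own wording. It warrants a wording change but does not threaten the trial's main conclusions. Per affected patient the week-8 estimate falls by up to 5 points (Part 2B) or 10 points (Part 2A), always in the direction of shorter PFS and TTP, and by less than one standard error at the assumed week-8 values. This assumes that all planned patients are analysed and none is censored earlier.

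Three stronger conclusions are not supported:

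- That Part 2 PFS will be materially biased. No rate of unconfirmed bone findings is given, and many affected patients would progress later anyway, so most of the effect is earlier dating.
- That Part 1 has the same fault. The adjoining column of the Section 6 table is redacted.
- That OS is censored wrongly. SAP 6.3.1 says last visit and 9.2 has no OS row, but telephone survival follow-up is a scheduled activity and may be what is meant. Only the wording needs clarifying.

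**What to change.** **SAP Section 6.** Replace the footnote with: *For mCRPC, bone progression counts as an event for PFS, TTP and the end of DOR only if confirmed per Section 9.5, dated at first detection; soft-tissue progression follows Section 9.5 (no confirmation).*

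**SAP 9.2.** Add two rows to Tables 1 and 2:

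- Bone finding not confirmed: no event, and follow-up continues.
- Bone finding with no later bone scan: not an event by itself. The other rows apply: soft-tissue progression, death for PFS and DOR, otherwise censoring at the last objective tumor assessment.

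**Protocol 7.8.** Reconcile its confirmation requirement with Appendix 7 for endpoint purposes, without changing any treatment rule.

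Keeping the unconfirmed analysis as a sensitivity analysis is optional. As a separate minor edit, state in SAP 6.3.1 whether telephone contacts count as a visit for OS censoring.

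The cost is SAP text and one protocol clarification. No new scans are needed: footnote 20 of the Part 2A and 2B schedules already plans bone scans every 8 weeks for the first 24 weeks, which includes week 16. Protocol 7.8 also speaks of bone scans when medically indicated; if that leaves a patient without a later scan, the second new row applies.

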6.1. Standard Analyses

Study Conduct and Patient Disposition

An accounting of the study patients will be tabulated. The subject evaluation groups will be listed. The Full Analysis Set will be used.

Subject discontinuation from treatment and study will be tabulated and listed separately with their reason for discontinuation. The Safety Analysis Set will be used.

Baseline Characteristics

Baseline characteristics such as demographics, prior medication, medical history, ECOG performance status, and primary diagnosis will be tabulated and listed. For ECOG

performance status a shift table (worst post-baseline vs baseline may be produced). The Safety Analysis Set will be used.

Treatment Administration/Compliance

Listings and tables by dose level will be provided. Cycle length is 28 days (± 2 days) for oral administration. Day 1 of a cycle is the first date of dose within that cycle. The safety analysis set will be used.

Dose modifications may occur in the following ways:

- Cycle delay—Day 1 of current cycle starts later than 28 (+2) days from Day 1 of the previous cycle (only applies to cycle 2 and above), will be used in determining cycle delay. For example, after cycle 1 ended for a patient in Part 1, a new cycle didn't start until 28 (+2) days after (but before 56 days after) cycle 1 day 1, the newly started cycle will be considered as cycle 2, and cycle 2 is considered delayed.
- Cycle skip – Day 1 of current cycle starts later than 56 (+4) days from Day 1 of the previous cycle (only applies to cycle 2 and above). For example, After cycle 1 ended for a patient in Part 2, a new cycle didn't start until 56 (+4) days after cycle 1 day 1, the newly started cycle will be considered as cycle 3, and cycle 2 is considered skipped for this patient.
- Dose reduction—a decrease in the administered total daily dose (non-zero) compared to the planned total daily dose upon enrollment. If in the CRF the prescribed dose unit is mg/kg, but the actual dose is in mg the actual dose mg/kg should be calculated considering the body weight of the patient at that visit. Intrapatient dose reductions are not permitted during the study unless, in discussion with the sponsor, a dose level is deemed beyond the determined MTD.
- Dose interruption – a skip in the planned administered daily dose upon enrollment. It includes missed dose and the dose with 0 administered collected on the CRF.

The following will be summarized for each dose level:

- Number of subjects;
- Number of cycles per subject
- Number (%) of subjects with cycle delays and cycle skips;
- Number (%) of subjects with dose interruptions;
- Number (%) of subjects with dose reductions;
- Number (%) of each reason (drug related AE vs AE vs. Other) for cycle delays, dose interruptions and dose reductions;
- Time on treatment (median, range).

- Number of cycles before 1st delay (median, range);
- Number of cycles before 1st reduction (median, range);
- Number of cycles before 1st interruption (median, range).

The following will be summarized for cumulative dose by dose level and cycle:

- Summary statistics (mean, median, standard deviation and range) of cumulative dose and percent of starting dose (compared to Day 1 dose of each cycle).

Listings by subject (ordered by dose level): start date and stop date of each dosing period within each cycle (including records with 0 mg), administered total daily dose for each period, any missed doses with unknown dates (Y/N), number of missed doses with unknown dates, reason for any dosing changes.

Listings by subject and each cycle (ordered by dose level): cycle length, total planned dose, administered total dose, percentage of planned dose, dose delay (yes/no), dose reduction (yes/no), and dose interruption (yes/no).

Prior, Concomitant, and Further Therapies

Prior, concomitant, and further therapies (drug and non-drug treatments) will be coded by the World Health Organization (WHO) medical dictionary. Listings of prior, concomitant, and further therapies will be provided separately.

6.2. Analysis of Primary Endpoint

6.2.1. DLT (Part 1 and Part 2)

Dose Limiting Toxicity is the primary endpoint of the dose escalation phase of the study, which will be summarized by dose level using the Per Protocol Analysis Set for patients in the dose escalation portion of the study. A listing of the DLTs will also be provided. If necessary, a summary and listing of the DLT by malignancy may be provided using the Per Protocol Analysis Set for patients in the MTD expansion portion of the study.

6.2.2. Safety Endpoints (Part 1 and Part 2)

Adverse Events

Adverse Events (AEs) will be graded by the investigator according to the CTCAE version 5.0 and coded using the MedDRA.⁸ The focus of AE summaries will be on Treatment Emergent Adverse Events (TEAE), which is defined as any adverse event that occurs after the beginning of the study treatment (on or after Study Day 1) or any pre-existing adverse event that worsens after the beginning of the study treatment and at least 28 days after final dose of study treatment or start of new anticancer therapy (whichever comes first). The number and percentage of patients who experienced any AE, serious AE (SAE), treatment related AE, and treatment related SAE will be summarized according to worst toxicity grades. The Safety Analysis Set will be used. Part 1 and Part 2 data will be

summarized separately and may also be pooled together for analysis. Pfizer standard on safety data reporting will be followed.

Laboratory Tests Abnormalities

The number and percentage of patients who experienced laboratory test abnormalities (including liver function test) will be summarized according to worst toxicity grade observed for each laboratory test for overall and each dose. The analyses will summarize laboratory tests both in the entire study period and by cycle (Cycle 1 and Cycles beyond 1). Shift tables will be provided to examine the distribution of laboratory abnormalities. The Safety Analysis Set will be used.

For laboratory tests without CTC grade definitions, results will be categorized as normal, abnormal high/low or not done.

